In this document, the approach to the sample size and statistical analyses are outlined for the Dual hormone closed loop in type 1 diabetes: a randomized trial (DARE). This statistical analysis plan was written in accordance with research protocol version 7.0 dated 29-05-2024.

The DARE trial is a 12 month open-label, two-arm randomised parallel-group trial aiming to determine in patients with type 1 diabetes (T1DM) the long-term effectiveness of treatment with a dual-hormone (insulin and glucagon) fully closed loop system (DHFCL) during 12 months compared to both the current most advanced technological care and to the currently most used care. The study consists of 240 patients in total, with study arm 1 including 170 patients randomised to either DHFCL (index) or a hybrid closed loop (HCL) as control, and study arm 2 with in total 70 patients randomised to either DHFCL (index) or multiple daily injections (MDI) in combination with continuous or flash glucose monitoring (CGM or FGM) as control. In both arms, patients are 1:1 randomised to either receiving the DHFCL (index group) or continuation of their current treatment (control group), stratified by participating study centre. Thus, from the 170 patients on HCL, 85 will be randomised to the DHFCL treatment and 85 will continue their HCL treatment. Likewise, from the 70 MDI patients, 35 will be randomised to DHFCL and 35 patients to continue their MDI treatment.

All patients will be asked to wear a blinded sensor (FSL Pro IQ, Abbott) to measure glucose levels at baseline, 3, 6, 9 and 12 months.

The primary endpoint is the time in range (TIR; % of time spent between 3.9-10 mmol/l) at 12 months. Secondary endpoints include other glycaemic endpoints such as time above and below range (TAR and TBR, respectively) and glycaemic variability, patient reported outcome measurements (PROMs), cost effectiveness outcomes and safety and device-related outcomes.

2. Statistical hypothesis

The primary outcome is:

- Superiority in the Time in Range (TIR; % of time spent in the 3.9-10 mmol/l target range) at 12 months

There is no key secondary outcome. All secondary outcomes are described in section 4 (P7-9). The primary analysis will be performed for each of the study arms separately (i.e. DHFCL vs HCL, and DHFCL vs MDI).

Time in range outcome study arm 1 - HCL as control treatment and DHFCL as index treatment:

- Null hypothesis: There is no difference in the mean TIR at 12 months between DHFCL and HCL group
- Alternative hypothesis: there is a nonzero difference in the mean TIR at 12 months between DHFCL and HCL group

Time in range outcome study arm 2 - MDI+FGM/CGM as control treatment and DHFCL as index treatment:

- Null hypothesis: There is no difference in the mean TIR at 12 months between DHFCL and MDI+FGM/CGM group
- Alternative hypothesis: there is a nonzero difference in the mean TIR at 12 months between DHFCL and MDI+FGM/CGM group

3. Sample size

3.1 Study arm 1: HCL as control treatment and DHFCL as index treatment

A recent cross over study of the index intervention treatment (DHFCL) showed a median mean TIR of 86% (SD 4%).¹ Previous studies show a mean TIR under HCL treatment of 70 to 78% (SD 16% to 17%). ²⁻⁴ To be conservative, we assume a 7% increase in mean TIR from 78% under the HCL control treatment (SD 17%) to 85% under the index intervention treatment (SD 4%), using the two sample t-test with unequal variances, two-sided significance level of 0.05 and a power of 90%. Accordingly, the required sample size for this arm is 68 per group. To allow for potential loss to follow-up and to address the main secondary endpoints, we include a sample size of 85 per group in this arm of the trial: 85 in the HCL control treatment group and 85 in the DHFCL index treatment group.

3.2 Study arm 2: MDI+FGM/CGM as control treatment and DHFCL as index treatment.

Previous studies showed a mean TIR under MDI+FGM/CGM treatment of 50-59% (SD of 12 to 20%).⁵ To be conservative again, we assume a mean TIR in the MDI+FGM/CGM control group of 70% (SD 20%) and for the DHFCL index intervention of 85% (SD 4%) (similarly as above), thus assuming a 15% increase in mean TIR due to the index intervention. Using the two sample t-test with unequal variances, two-sided significance level of 0.05 and a power of 90%, the required sample size for this arm is 22 per group. To allow for potential loss to follow-up and to address the main secondary endpoints we include a sample size of 35 per group in this arm of the trial: 35 in the MDI+FGM/CGM control treatment group and 35 in the DHFCL index treatment group.

4. Outcome measures

4.1 Primary endpoint

• The main study endpoint is the time in range (TIR; % of time spent in the 3.9-10 mmol/l target range) at 12 months.

4.2 Secondary endpoints

Secondary endpoints include other glycaemic outcomes, patient reported outcome measurements, and cost-effectiveness outcomes and safety and device-related outcomes.

4.2.1 Glycaemic control endpoints at 0, 3, 6, 9 and 12 months:

- Time in range (TIR) (3.9-10 mmol/l) (%; amount of time (hours/minutes)) at 3, 6 and 9 months;
- Time above range (TAR):
 - level 1 and 2 hyperglycaemia: % of time spent >10.0 mmol/l;
 - level 2 hyperglycaemia: % of time spent >13.9 mmol/l;
- Time below range (TBR):
 - level 1 and 2 hypoglycaemia: % of time spent <3.9 mmol/l;
 - level 2 hypoglycaemia: % of time spent <3.0 mmol/l;
- Number of hypoglycaemic events: defined as glucose <3.0 mmol/l for 15 consecutive minutes⁶, when the time between two successive events is less than 30 minutes, they will be combined and counted as one event;
- Mean glucose (mmol/l) per patient per time point:
 - o day and night;
 - o day: from 06:00 to 23:59 hours;
 - night: from 00:00 to 05:59 hours;
- Glycaemic variability:
 - Coefficient of variation (%);
 - Standard deviation (mmol/l);
- HbA1c:
 - Mean per patient per time point (mmol/mol);
 - Percentage of patients achieving HbA1c \leq 53 mmol/mol.
- Percentage patients with ≥5% points TIR improvement from baseline (%) at 12 months;
- Percentage patients achieving >70% TIR and/or <4% TBR at 12 months;
- Time in tight range (3.9-7.8 mmol/l) (%; amount of time (hours/minutes).

4.2.2 Patient reported outcome measures (PROMs), at 0, 3, 6, 9 and 12 months:

- World Health Organization-Five Well-Being Index (WHO-5) score;
- Health-related quality of life scores (EQ-5D-5L);
- Diabetes Treatment and Satisfaction Questionnaire status and change (DTSQ-s and DTSQ-c) scores;
- Problem Areas In Diabetes (PAID-5) score;
- Hypoglycaemia Fear Survey-II (HFS-II) Worry subscale score;
- Pittsburgh Sleep Quality Index (PSQI) score;

- Insulin delivery systems: perceptions, ideas, reflections and expectations (INSPIRE) scores; only for HCL and DHFCL groups;
- Hypoglycaemia unawareness (Gold-Clarke): only at 0 and 12 months.

These scores will be calculated as defined previously.^{8–16}

4.2.3 Cost effectiveness endpoints:

- Medical Consumption Questionnaire (MCQ), at 0, 3, 6, 9 and 12 months;
- Productivity Cost Questionnaire (PCQ), at 0, 3, 6, 9 and 12 months;
- Detailed hospital health care consumption for each individual patient (collected from electronic patient files, including frequency of unplanned patient contact with the diabetes team);
- Cost effectiveness: cost per quality adjusted life year.

4.2.4 DHFCL endpoints, at 3, 6, 9 and 12 months:

- Daily glucagon use (mg/day);
- Percentage of time the control algorithm was active while wearing the DHFCL device. For this calculation, we will use the algorithm status output that is logged every 10 minutes while the DHFCL was in use.

4.3 Safety and other endpoints

- Adverse events and serious adverse events ((S)AEs);
- Device issues;
- Aspartate aminotransferase (ASAT) (U/L) and alanine aminotransferase (ALAT) (U/L) at 12 months;
- NSAID use (due to excluded daily acetaminophen use) and associated drug complications (e.g. stomach ulcers) rate;
- Daily insulin use at 3, 6, 9 and 12 months (UI/day);
- Weight (kg), blood pressure (mmHg) and pulse (beats/min) at 12 months;
- Frequency of unplanned patient contact with the diabetes team;
- Concomitant medication, at screening, baseline, 3, 6, 9 and 12 months;
- Continuation rate: expressed as the percentage of participants that continue DHFCL treatment after 1 year of use;
- Reasons for discontinuation of the DHFCL treatment;
- Glycaemic data for at least 70% of the collection period of 14 days (N, %: see section 4, 4.1, and 5.1 for details).
- Glycaemic data for at least 50% of the collection period of 14 days (N, %: see section 4, 4.1, and 5.1 for details).

4.4 Definitions safety parameters

Safety parameters include AEs, SAEs and device-related issues.

AEs are defined as any undesirable experience occurring to a subject during the study, whether or not considered related to the DHFCL. AEs of special interest include:

- Events possibly related to glucagon or fluctuating glucose levels: nausea/fatigue/headache/restlessness;
- Skin reaction tape infusion set: erythema/discomfort/irritation/rash;
- Reaction infusion set/site: discomfort/inflammation/pain/lipodystrophy;
- Skin reaction tape glucose sensor: erythema/discomfort/irritation/rash/ damage;
- Reaction glucose sensor (insertion site): bruising/bleeding/pain.
- New diabetes complications;
- Deterioration (from baseline) of diabetes complications;
- Ketoacidosis;
- Severe hypoglycaemia (hypoglycaemia that leads to a seizure or unconsciousness),

Hypoglycaemia is a disease specific endpoint, and not recorded as AE in this trial.

SAEs are defined as any untoward medical occurrence or effect that

- results in death;
- is life threatening (at the time of the event);
- requires hospitalisation or prolongation of existing inpatients' hospitalisation;
- results in persistent or significant disability or incapacity;
- is a congenital anomaly or birth defect; or
- any other important medical event that did not result in any of the outcomes listed above due to medical or surgical intervention but could have been based upon appropriate judgement by the investigator.

An elective hospital admission will not be considered as a SAE.

Device incidents are defined as any malfunction or deterioration in the characteristics or performance of the DHFCL system, including use-error due to ergonomic features, as well as any inadequacy in the information supplied by the manufacturer and any undesirable side-effect.

5. Analysis datasets and statistical analyses

The primary and secondary analyses will be performed on an intention-to-treat (ITT) principle and per-protocol (PP) principle. All randomized participants will be analyzed for the ITT analysis and all safety analyses.

The PP analysis will be limited to visits of patients that adhered to the randomised treatment. For example, a patient that adhered to the treatment regime up to 6 months of follow-up and subsequently changed the treatment regime will be included until the 6 month visit. All subsequent visits will be excluded from the PP analyses, also when patients returned to the randomized treatment later in the follow-up. The PP analysis will also be restricted to participants with:

- No glucose-lowering medications used other than those acceptable in the protocol;
- For participants in the DHCL group, closed loop mode is active for at least 80% of the time during the trial duration before drop-out (if any)

This PP analysis will only be done if >5% of the participants are excluded based on these criteria.

The primary outcome is measured with a blinded sensor with the aim to collect 14 consecutive days of glucose measurements. However, not all patients may be able or willing to provide continuous glucose measurements for 14 days. This will be further evaluated with sensitivity analyses.

5.1 Analysis of the primary endpoint

The primary analysis will be performed for each of the study arms separately (i.e. DHFCL vs HCL, and DHFCL vs MDI) and will follow the ITT principle with the data from each participant analysed according to the treatment assigned by randomization.

Included subjects

All subjects who had at least ≥ 168 hour of blinded sensor data (i.e. 50%) at baseline and at least one follow-up visit.⁷ Valid measurements of primary outcomes at any visit will be included in the analyses: for example, a patient with a missing 6 month measurement (for any reason) and valid measurements at subsequent visits will be included in the analysis with all available measurements. If the subject has <168 hours of sensor data, then the baseline metrics will not be calculated and will be set to missing. Likewise, if a subject has <168 hours of sensor data, then post-randomization sensor metrics will not be calculated and will be set to missing.

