7.1 Baseline variables

Multiple imputation will be applied for missing values on baseline variables that may be used in any of the statistical analyses. Prior to the imputation, an analysis will be conducted to evaluate associations between the occurrence of missing values and available patient and disease characteristics.

Multiple imputation will be applied with a fully conditional specification and performed for control groups and intervention groups separately,²³ with a correction for clustering in centers of inclusion. Initial imputations will be performed on data in a so-called wide format, where all measurements over time are included as separate variables. The logistic regression approach will be used for categorical variables, continuous measurements will be imputed with predictive mean matching. The imputation of baseline variables will be performed on all variables that will be included in the statistical analysis including primary and secondary outcomes at baseline and at follow-up. Additionally, other observed variables considered to be associated with missing values will be included in the imputation. The number of imputations will initially be equal to the percentage of patients with missing data on variables to be included in any analysis plus 10. When this percentage is below 10%, a minimum of 20 imputations will be used. When the percentage of patients with missing patients is larger than 50%, the number of imputations will be increased to 100.^{24,25}

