7.2 Missing primary and secondary outcome measurements

A blinded sensor is used for measuring the primary endpoint. Patients with at least 168 hours of sensor data on a specific follow-up time will be included in the analyses. All valid TIR measurements at a specific time point during follow-up will be included in the analysis, also for patients with incomplete follow-up. Sensitivity analyses on the primary endpoint will be conducted to assess the impact of incomplete sensor measurements. Based on the consensus statement on glucose sensor measurement,⁷ analyses will be repeated by calculating the TIR based on the first 235.2 hours (i.e. 70% of 14 days) of sensor measurements for all patients, excluding patients with less than 235.2 hours of sensor data.

Even though primary and secondary outcomes will be included in the imputation of baseline variables, the imputed values of outcomes will not be included in the primary analysis, as this may result in biased estimation of treatment effect or loss of efficiency.^{24,26} For patients with missing outcomes due to intolerability of the DHFCL, a separate imputation and sensitivity analyses of primary and secondary outcomes is specified in the section on drop-outs (section 7.3). In these sensitivity analyses, imputed outcomes will be included. Patients with incomplete baseline variables that drop-out early after randomisation (i.e. prior to the measurement at 3 months) may be fully excluded.

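### The inclusion rule in SAP section 5.1 requires 168 h of baseline sensor data, which contradicts the all-randomised ITT set in section 5

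*SAP*

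**What the plan says.** Section 5 defines the ITT set without conditions: "All randomized participants will be analyzed for the ITT analysis and all safety analyses". Section 5.1 states that the primary analysis follows ITT. Its paragraph on included subjects then admits those with at least 168 h "of blinded sensor data (i.e. 50%) at baseline and at least one follow-up visit".

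The same paragraph says "Valid measurements of primary outcomes at any visit will be included in the analyses". If a baseline recording is shorter than 168 h, "then the baseline metrics will not be calculated and will be set to missing".

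Section 7.1 deals with missing baseline values: "Multiple imputation will be applied for missing values on baseline variables that may be used in any of the statistical analyses". It counts the primary outcome at baseline among the variables in that imputation.

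Section 7.2 gives the rule for follow-up: "Patients with at least 168 hours of sensor data on a specific follow-up time will be included in the analyses", and "All valid TIR measurements at a specific time point during follow-up will be included in the analysis". It closes with a permissive sentence: "Patients with incomplete baseline variables that drop-out early after randomisation (i.e. prior to the measurement at 3 months) may be fully excluded".

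Section 6.1 specifies two models. The first has time, treatment and their interaction. The second adds baseline TIR, age and sex.

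**The concern.** The baseline condition in 5.1 and the unconditional statement in section 5 cannot both define the primary analysis set, and the SAP gives no order of precedence. Two statisticians could each follow the text and report different patient numbers, estimates and p-values. Under 6.1, p-values are reported only for the primary ITT analysis, so this set carries the confirmatory result. The trial is open-label, so the choice should be closed before anyone sees outcome data.

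Read literally, 5.1 also discards observed 12-month outcomes because a baseline covariate is incomplete. That differs from the usual and unavoidable absence of patients who have no outcome at all.

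**Working it through.** **Step 1. Follow one patient through the text.** Take a randomised patient with 150 h at baseline and valid TIR at 3, 6, 9 and 12 months.

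| Place in SAP | Consequence | Type of statement |
|---|---|---|
| 5 | in | express |
| 5.1, included subjects | out | express |
| 5.1, metrics under 168 h | baseline TIR set to missing, which has no role in the primary analysis if the patient is already out | implied: in |
| 7.1 | baseline TIR imputed | implied: in |
| 7.2 | follow-up TIR valid and used; no baseline condition mentioned | implied: in |

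It is unclear whether the 168 h in 5.1 also applies to the follow-up visit. On either reading it applies at baseline, so the patient is out. The express contradiction is between 5.1 and 5; the other conflicts are by implication.

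**Step 2. Is the baseline condition needed?** The first model in 6.1 has no baseline TIR term. The second does, and 7.1 supplies imputed values for it. Neither model needs the exclusion.

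**Step 3. Reproduce the plan's sample sizes.** Inputs from section 3: arm 1 difference 7, SD 17 and 4; arm 2 difference 15, SD 20 and 4; two-sided 0.05; power 90%; Welch t-test. With n per group, SE = √((s₁² + s₂²)/n). Degrees of freedom are Satterthwaite's and power comes from the non-central t distribution. The smallest n with at least 90% power is 68 in arm 1 (90.4%) and 22 in arm 2 (91.0%), as stated.

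**Step 4. Size of the loss.** The SAP gives no rate of baseline recordings under 168 h. Exclusion of 5%, 10% or 20%, equal in both groups and with no other loss, is an assumption. Half-width = t(0.975, df) × SE. For arm 1 at n = 85: SE = √(305/85) = 1.894, df = 93.3, t = 1.986, half-width = 3.76.

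| Arm | Excluded | n per group | Half-width (TIR points) | Widening | Power |
|---|---|---|---|---|---|
| 1 | none | 85 | 3.76 | – | 95.5% |
| 1 | about 5% | 81 | 3.86 | 2.5% | 94.6% |
| 1 | about 10% | 76 | 3.98 | 5.9% | 93.2% |
| 1 | 20% | 68 | 4.22 | 12% | 90.4% |
| 2 | none | 35 | 6.99 | – | 98.9% |
| 2 | about 5% | 33 | 7.21 | 3.2% | 98.4% |
| 2 | about 10% | 31 | 7.46 | 6.7% | 97.8% |
| 2 | 20% | 28 | 7.88 | 13% | 96.4% |

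**Step 5. Does this carry over to the planned model?** With complete follow-up and equal groups, the 12-month contrast from a model with time, treatment and their interaction has the standard error of the raw difference in 12-month means. Generalised least squares with heterogeneous autoregressive residuals, leaving out the centre intercept, used a common 12-month SD of √((17² + 4²)/2) = 12.35. It gave 1.894 at n = 85 and 2.118 at n = 68, the same as Welch.

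**Step 6. The margin.** Arm 1 has 85 − 68 = 17 per group to spare, and section 3.1 assigns that margin to loss to follow-up and the main secondary endpoints. Baseline exclusions use the same margin. At 67 per group, power is 89.9%. Arm 2 has 35 − 22 = 13 per group to spare.

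**The case against.** The strongest reply is that the intention is fairly clear. One badly worded sentence stands against the set-to-missing rule, the imputation in 7.1 and the follow-up rule in 7.2, and a sensible analyst would keep these patients. That stands as a guide to which way to amend. It does not settle the matter, because the sentence in 5.1 is the only one that sets out to list who is in the primary analysis.

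A reader might infer more than the document supports in four places:

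- *That 7.2 expressly contradicts 5.1.* Section 7.2 concerns missing outcomes and is silent on baseline recordings when it sets its rule. The conflict is implied.
- *That the closing sentence of 7.2 leaves the primary result open.* A patient who leaves before the 3-month measurement has no follow-up TIR, and the primary analysis does not use imputed outcomes. Keeping or excluding that patient leaves the primary estimate unchanged.
- *That the rule biases the comparison.* The condition is the same in both groups and concerns baseline. Bias is unlikely if the recording is made before allocation is known. The SAP does not state that timing, so this remains an assumption.
- *That power is safe, or that it is lost.* Power of at least 90% at 20% exclusion holds only if there is no other loss. The SAP gives no figure that shows a shortfall either.

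It is also fair to say that any likelihood-based analysis omits patients with no valid follow-up TIR. The point here concerns only those whose outcomes were observed.

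**Conclusion.** The contradiction is real: the inclusion rule in 5.1 is incompatible with the ITT set in section 5 and fits poorly with 5.1's own missing-data rule, 7.1 and 7.2. Its cost is an analysis set that is not fixed, incomplete ITT and a modest loss of precision. At the assumed 5% to 20% exclusion, intervals are about 2.5% to 12% wider in arm 1 and 3% to 13% wider in arm 2. These figures rest on the section 3 SDs, equal exclusion in both groups and no other loss. The true number affected is unknown and may be small. The text should be corrected before the data are seen; nothing in the document shows bias or a failure of power.

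**What to change.** Wording changes only:

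- **Section 5.1**, replace the inclusion sentence: 'All randomised patients with at least one valid (at least 168 h) post-randomisation TIR measurement, analysed as randomised; baseline TIR based on under 168 h is set to missing and imputed per 7.1 for the adjusted model.'
- **Section 5**, add: 'Patients with no valid post-randomisation TIR contribute no outcome to the primary mixed model; their number is reported per group.'
- **Section 7.2**, replace the last sentence: 'In the primary analysis (without imputed outcomes), patients without any valid post-randomisation measurement contribute no data; incomplete baseline variables alone are not a reason for exclusion. The sensitivity analyses of 7.3 are unaffected.' The limit to the primary analysis is needed because 7.3.1 imputes and analyses outcomes of patients who withdraw.
- **Reporting**: give the number with under 168 h at baseline, per group. Section 4.3 already lists a count at the 50% threshold but names neither the baseline visit nor reporting by group.

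The complete-baseline set may be kept as a sensitivity analysis. The imputation of baseline TIR is already planned, so no new data or methods are needed.
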